11.3.2 Macroscopic urinalysis

Quantitative urinalysis parameters will be summarized in the same manner as hematology and blood chemistry parameters. Response categories are negative, 1+, 2+, and 3+ for the qualitative urinalysis parameters occult blood, leukocytes, glucose, protein, and ketones and negative and positive for nitrates. Outcome values for these parameters are mapped to the levels Negative, 1+, 2+, and 3+ as follows for purposes of summary tables and the determination of PCST:

| Category | Definition |
|----------|---|
| Negative | “Negative”, “NEGATIVE”, or other outcomes that clearly reflect a negative finding |
| 1+ | “1+”, “+”, “Trace”, “TRACE”, or other outcomes that clearly reflect trace amount |
| 2+ | “2+” or “++” |
| 3+ | “3+”, “+++”, or other outcomes that clearly reflect the data above 3+ (eg, “4+”, “5+” etc) or more than 4 plus signs (eg, “++++”, “+++++”etc) |

For qualitative urinalysis parameters (occult blood, leukocytes, glucose, protein, ketones, and nitrates), the number and percentage of subjects with each response category will be summarized for Baseline, Study Entry, each scheduled visit during the Evaluation Period for which urinalysis parameters were scheduled to be assessed, Last Value, EDV, and FV. Percentages for each parameter will be relative to the number of subjects with a result at each time point.

For occult blood, leukocytes, glucose, protein, ketones, and nitrates, the number and percentage of subjects with an on-treatment PCST value, PCST low value, and PCST high value will be summarized. This summary will consider all assessments after the first dose of BRV and prior to or on the date of the last dose of BRV. Percentages will be relative to the number of subjects with an on-treatment assessment.

Additionally, for occult blood, leukocytes, glucose, protein, ketones, and nitrates, the number and percentage of subjects with a PCST value, PCST low value, and PCST high value will be summarized for Baseline, Study Entry, each visit during the Evaluation Period for which laboratory parameters were scheduled to be assessed, EDV, Last Value, and FV. Percentages for each parameter and time point will be relative to the number of subjects with a value at that time point.

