- Urinalysis: specific gravity, pH, glucose, bilirubin, ketones, occult blood, protein, nitrites, leukocytes. If the test for protein, blood or leukocytes shows a trace or is positive, sediment and microscopic analyses (erythrocyte cast, leukocyte casts, hemoglobin casts, uric acid crystals, biphosphate calcium oxalate crystals, monohydrate calcium oxalate crystals, triple phosphate crystals and bacteria) will be conducted.
- Where applicable (women of childbearing potential), a urine pregnancy test will be conducted.

Plasma samples to analyze BRV and concomitant AED plasma concentrations will no longer be obtained.

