2.4 Determination of Sample Size

No sample size calculation was done. Sample size was dependent upon recruitment into and completion of preceding studies. At the time of development of this SAP, the study enrollment has been completed; a total of 668 subjects were enrolled into N01199.

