13.3.3 Urinalysis

Qualitative urine parameters are generally reported by a descriptive score, which differs among laboratories. For data analysis purpose, a four-point scale is used. Five-point, six-point, or seven-point scales will be collapsed into a four-point scale first. A value is considered possibly clinically significant treatment emergent abnormal if an upward shift of at least 2 degrees from the baseline occurs under investigational treatment. To collapse the results in a five-point scale into a four-point scale, the lowest two positive results will be combined (see example below). For results reported with a scale of more than five-point, please consult your study physician for how to collapse into four-point scale.

| Original Five-point Scale | Four-point Scale |
|---------------------------|--------------------------|
| Negative/None | Negative/None |
| Trace/Rare/Mild/A Few | Trace/1+/Rare/Mild/A Few |
| 1+ | |
| 2+/Mod | 2+/Mod |
| 3+/Sev | 3+/Sev |

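### The nitrite (SAP: nitrates) PCST count is zero by construction, because a negative/positive result cannot rise by the two degrees that the only urinalysis criterion requires

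*SAP*

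**What the plan says.** Protocol 11.1.14 lists the urine tests: "Urinalysis: specific gravity, pH, glucose, bilirubin, ketones, occult blood, protein, nitrites, leukocytes".

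SAP 11.3.2 (Macroscopic urinalysis) sets two kinds of scale. For five tests, "Response categories are negative, 1+, 2+, and 3+ for the qualitative urinalysis parameters occult blood, leukocytes, glucose, protein, and ketones". For the sixth the categories are "negative and positive for nitrates". The next sentence covers how PCST is to be determined: "Outcome values for these parameters are mapped to the levels Negative, 1+, 2+, and 3+ as follows for purposes of summary tables and the determination". The table that follows has rows for Negative, 1+, 2+ and 3+, and none of them mentions a result reported as positive.

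The same section then plans the PCST summary for all six tests together: "For occult blood, leukocytes, glucose, protein, ketones, and nitrates, the number and percentage of subjects with an on-treatment PCST value", with low and high versions, and the same again by time point.

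The criterion is in SAP 13.3.3 (Urinalysis). It says "For data analysis purpose, a four-point scale is used" and counts a value as treatment-emergent abnormal "if an upward shift of at least 2 degrees from the baseline occurs under investigational treatment". It explains how to collapse scales longer than four points. It says nothing about a scale shorter than four points.

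**The concern.** The plan applies one threshold to six tests, and one of the six does not have enough levels to reach it. If every subject who was negative at Baseline became positive on treatment, the rule as written would still flag nobody.

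The table would show 0% beside five rows in which 0% is a finding. A reader of the study report could not tell that this row was fixed before any data were collected. Long-term safety is the primary objective, so a safety row that cannot respond to the data should not be printed as a result.

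**Working it through.** The SAP gives no figure for this row, so there is nothing to reproduce. The check is an enumeration.

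**Inputs**
- Nitrate/nitrite scale: 2 levels (SAP 11.3.2).
- Scale for occult blood, leukocytes, glucose, protein and ketones: 4 levels (SAP 11.3.2).
- Criterion: on-treatment level minus Baseline level must be 2 or more (SAP 13.3.3).

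**Two-level scale.** Code negative = 0 and positive = 1. There are 2 × 2 = 4 possible (Baseline, on-treatment) pairs:
- (0,0): shift 0
- (0,1): shift 1
- (1,0): shift −1
- (1,1): shift 0

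The largest shift is 1, which is below 2. Qualifying pairs: 0 of 4. The count is zero for any data.

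**Four-level scale.** Code Negative, 1+, 2+, 3+ as 0 to 3. There are 4 × 4 = 16 pairs, and the largest shift is 3. The qualifying pairs are Negative to 2+, Negative to 3+ and 1+ to 3+, that is 3 of 16. The rule therefore works for the other five tests.

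**Does the mapping table rescue the sixth?** Suppose the mapping sentence is meant to include nitrates, so that a positive result must be given one of the four levels:
- Positive at 1+: negative to positive is a shift of 1. Qualifying pairs: none. The count stays at zero.
- Positive at 2+: shift of 2. Negative to positive qualifies.
- Positive at 3+: shift of 3. Negative to positive qualifies.

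No row of the table and no sentence in 13.3.3 assigns positive to 2+ or 3+. A non-zero count would need a programming decision that the SAP does not record.

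**What the row would otherwise show.** Under a negative-to-positive rule, 1 of the 4 two-level pairs qualifies, and the count equals the number of subjects who convert. The documents give no conversion rate. For assumed rates of 1%, 5% and 10%, it would be 1, 5 and 10 per 100 subjects assessed, against 0 per 100 under the written rule.

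**The case against.** The strongest reply is that 11.3.2 determines PCST after mapping to four levels, so the fault is an undefined mapping and not a proven zero. Part of this stands. A reader might infer that no value other than 0% could ever be printed. The documents do not support that in full, because a programmer who placed positive at 2+ or 3+ would obtain a count. But the SAP does not authorise that placement, and the literal two-level reading and placement at 1+ both give zero. Either way a rule has to be written down.

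The second reply concerns importance, and it stands. SAP 11.3.2 also tabulates each response category, nitrates included, at Baseline, Study Entry, each scheduled visit, Last Value, EDV and FV. Subject listings are planned (SAP 3.1). Urinalysis is among the other safety variables and not the primary ones (SAP 2.2.1), and no hypothesis is tested. Positive results would not be hidden. What those tables do not provide is a link from each subject's result to that subject's own Baseline, which is the purpose of a treatment-emergent count.

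Three further inferences are tempting and should not be drawn:
- **That the result is 0 out of 668.** The SAP does say "a total of 668 subjects were enrolled into N01199", but the PCST denominator in 11.3.2 is subjects with an on-treatment assessment, or with a value at the time point. The documents give neither number.
- **That the PCST low columns are a second analysis error.** Only upward shifts qualify, so these columns must be empty for all six qualitative tests. The same value/low/high layout is used for blood chemistry, where AST, ALT, creatinine and total bilirubin also have only an upper limit (SAP 13.3.2). It is template layout and misstates nothing.
- **That the SAP analyses a different analyte.** Nitrates in 11.3.2 is a wording slip: Protocol 11.1.14 and SAP 11.3.3 both name nitrite, and the analyte is identifiable.

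**Conclusion.** The point holds as a minor one. For nitrite, the only PCST criterion in the SAP cannot be met on the scale that the SAP gives the test, so the planned on-treatment and by-visit counts are zero by construction. This rests on reading 11.3.2 and 13.3.3 as written, with no unstated assignment of a positive result to 2+ or 3+.

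One of six qualitative urine tests is affected, in descriptive tables only. The other five work as intended, and no efficacy result or primary safety variable is touched. The loss is the subject-level treatment-emergent count for nitrite, together with a printed 0% that could be mistaken for evidence.

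**What to change.** Amend SAP 13.3.3 in one of two ways:
- State a rule for the two-level test, for example that nitrite is counted when it is negative at Baseline and positive on treatment. Note beside the table that this is less stringent than the two-degree rule applied to the other five tests. The documents do not justify that threshold, so the sponsor should confirm that it is wanted.
- Or remove nitrite from the PCST summaries and report a Baseline-by-on-treatment shift table for it. This introduces no new significance threshold.

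In 11.3.2, state whether the four-level mapping applies to nitrite at all.

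As tidying only, use nitrite throughout and mark PCST low as not applicable for qualitative urinalysis.

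The cost is a few sentences in the SAP and the reprogramming of one row. No new data are needed, and study conduct does not change.

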11.3.3 Microscopic urinalysis

In microscopic urinalysis, a small sample of urine is centrifuged to remove the liquid. The sediment is then examined under a microscope. In the urinalysis laboratory test group, other than urinalysis parameters such as Bilirubin, Blood, Glucose, Ketone, Nitrite, pH, Protein, Specific Gravity, Total protein, Hemoglobin, Beta-HCG, Occult Blood, and Leukocytes, a listing of microscopic analysis parameters will be provided; no summaries of microscopic analysis findings are planned.

11.4 Vital signs, physical findings, and other observations related to safety

11.4.1 Vital signs

Vital signs are assessed at all FEVs, MEVs, YEVs, EDVs, and at FV, and may also be assessed at Unscheduled Visits. Body weight is assessed at all FEVs, YEVs, EDVs, and at FV, and may also be assessed at Unscheduled Visits.

Observed values for SBP, DBP, pulse rate, and body weight will be summarized for Baseline, Study Entry, each visit during the Evaluation Period for which vital signs or body weight were assessed, EDV, Last Value, and FV. Changes from Baseline for SBP, DBP, pulse rate, and body weight will be summarized for all post-Baseline time points.

The number and percentage of subjects with an on-treatment PCST value, PCST low value, and PCST high value will be summarized for SBP, DBP, pulse rate, and body weight. This summary will consider all assessments after the first dose of BRV and prior to or on the date of the last dose of BRV. Percentages will be relative to the number of subjects with an on-treatment assessment.

Additionally, the number and percentage of subjects with a PCST value, PCST low value, and PCST high value will be summarized for the above parameters for Study Entry, each visit during the Evaluation Period for which vital signs or body weight were scheduled to be assessed, Last Value, EDV, and FV. Percentages will be relative to the number of subjects with a value at each time point.

PCST criteria (Section 13.3.4) are based on FDA Division of Neuropharmacologic Drug Products guidelines with some UCB-defined additions.

11.4.2 Electrocardiograms

ECGs are assessed at all YEVs, EDVs, and at FV, and may also be assessed at Unscheduled Visits.

The number and percentage of subjects with no abnormality, an abnormal but not clinically significant finding, and a clinically significant finding will be summarized overall. This summary will consider all assessments after the first dose of BRV and prior to or on the date of the last dose of BRV. Percentages will be relative to the number of subjects with an on-treatment assessment.

Additionally, the number and percentage of subjects with no abnormality, an abnormal but not clinically significant finding, and a clinically significant finding will be summarized for Baseline, Study Entry, each visit during the Evaluation Period for which an ECG is scheduled to be performed, Last Value, EDV, and FV. Percentages will be relative to the number of subjects with an ECG assessment at each time point. Subjects are counted at most once at each time point based on the worst observed outcome across all abnormalities reported at that time point.

A subject number listing will be provided that identifies subjects with a clinically significant finding after the first dose of BRV for each type of ECG abnormality.

11.4.3 Physical examination

A listing of abnormal physical examination findings will be provided; no summaries of physical examination findings are planned.

11.4.4 Neurological examination

A listing of neurological examination findings will be provided; no summaries of neurological examination findings are planned.

11.4.5 Psychiatric and mental status

A listing of abnormal Psychiatric and Mental Status findings will be provided; no summaries of Psychiatric and Mental Status findings are planned.

11.4.6 HADS

The scoring algorithm for HADS is described in Section 3.8.3.

HADS is assessed at the following time points: Month 2, Month 6, Month 12, Month 18, and Month 24. HADS is not assessed for mentally impaired subjects and subjects from N01193. HADS is also assessed at EDVs for subjects who discontinue prior to the YEV at the end of the second year. Prior to protocol amendment 6, HADS may have been assessed for more than 2 years after study entry for some subjects. These additional assessments will not be summarized but will be provided in subject data listings.

Observed values for HADS depression and anxiety scores will be summarized for Baseline and Last Value for the Safety Analysis Set. Additionally, observed values will be summarized for Baseline and by visit for each study visit cohort. Change from Baseline will be summarized at each visit during the Evaluation Period.

For summaries of observed values at each time point, only subjects with a change from Baseline value at that time point will be summarized. Additionally, the mean and SD for each

Baseline score will be provided at each post-Baseline time point for subjects included in the summary of change from Baseline.

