#### **13.1.3 Statistical Evaluation**

- General considerations:

Summary statistics will consist of frequency tables for categorical variables and descriptive statistics (number of available observations, mean, median, standard deviation, minimum, maximum, 25th and 75th percentiles) for continuous variables.

The periods considered are:

- Evaluation Period (V1 until the last Evaluation Visit)
- Down-Titration Period
- Post-Treatment Period

Efficacy summaries will be created separately for the POS and PGS subpopulations within the efficacy population, and safety summaries will be created for the safety population.

- Baseline:

Baseline, whether efficacy or safety, will always refer to the original prior study pretreatment Baseline value. Baselines created and validated, as part of the prior study SAPs, will be copied and used by this study for all changes from baseline analyses.

- Study entry/disposition:

Subjects will be sufficiently described to enable a clear understanding of the populations and subpopulations and relevant demographics, disease, medical history, current treatment(s), as well as disposition. Historical and Baseline data will be copied from the prior study as required by the SAP.

- Seizure efficacy variables:

Analyses will be based upon the Efficacy Population. Summaries will be over the entire Evaluation Period and by 3-month periods over the Evaluation Period.

- QOLIE-31-P, HADS, EQ-5D, and socio-professional efficacy variables:

Analyses will be based upon the Efficacy Population and summarized by data collection scheduled visits and for the last Evaluation Period assessment during the first 2 years. Data collected after Year 2 are not planned to be summarized.

- Medical resource and indirect cost efficacy variables:

Analyses will be based upon the Efficacy Population and summarized by 3-month periods. Data collected after Year 2 are not planned to be summarized.

- Safety variables:

Analyses will be based upon the Safety Population. Summary tables will be presented over the Evaluation Period by time windows, by periods, and by categories of total duration of exposure.

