Treatment-emergent AEs will be summarized by categories of total duration of exposure, period, and Medical Dictionary for Regulatory Activities (MedDRA®) Primary System Organ Class (SOC), and Preferred Term in incidence tables. Separate tables will be provided by categories of total duration of exposure, for AEs leading to withdrawal from the study, and for SAEs.

This document contains information used to support all marketing authorization applications and any extensions or variations thereof.

Laboratory values, vital signs, and weight will be summarized by period and visit. Possibly clinically significant treatment-emergent abnormalities for laboratory values, vital signs, and weight will be listed and summarized by period and visit. Electrocardiogram abnormalities, as well as physical and neurological abnormalities, will also be listed by period and visit.

Hospital anxiety and depression scales will be analyzed for the POS and PGS subpopulations.

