2.1.3 Exploratory objectives

Exploratory objectives for subjects with POS/PGS:

- To explore medical resource use and indirect cost parameters for the first 2 years
- To obtain a description of the subject's self-reported health status for the first 2 years
- To explore the effects of BRV on the subject's Health-related Quality of Life (HRQoL), anxiety, and depression for the first 2 years
- To explore any change in the subject's socio-professional status for the first 2 years

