3.5 Analysis populations

3.5.1 Safety Population

The Safety Analysis Set will consist of all subjects who took at least 1 dose of study drug.

Summaries of demographics and baseline characteristics, medical history, AEDs, non-AEDs, HADS, , study drug exposure, and safety outcomes will be provided for the Safety Analysis Set.

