3.6 Treatment Assignment and Treatment Groups

This is an uncontrolled study in which all subjects receive BRV in doses that are optimally adjusted for each subject. Generally, statistical summaries will present all subjects combined as a single treatment arm unless otherwise indicated.

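### The protocol says HADS will be analysed for the POS and PGS subpopulations, but SAP 11.4.6 plans no HADS summary by seizure type and gives no reason

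*SAP*

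**What the plan says.** **Protocol.** Section 13.1.3 closes its text on safety variables with: "Hospital anxiety and depression scales will be analyzed for the POS and PGS subpopulations". Earlier in the same section, a bullet that names HADS alongside QOLIE-31-P and EQ-5D says: "Analyses will be based upon the Efficacy Population and summarized by data collection scheduled visits". The general considerations there add: "Efficacy summaries will be created separately for the POS and PGS subpopulations within the efficacy population". Section 13.1.1 defines POS and PGS as mutually exclusive groups.

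**SAP.** Section 3.5.1 includes HADS in the list that ends "study drug exposure, and safety outcomes will be provided for the Safety Analysis Set". Section 11.4.6 gives the HADS analyses: "Observed values for HADS depression and anxiety scores will be summarized for Baseline and Last Value for the Safety Analysis Set"; then "Additionally, observed values will be summarized for Baseline and by visit for each study visit cohort"; then change from Baseline at each Evaluation Period visit. Seizure type is not mentioned. The default in section 3.6 is: "Generally, statistical summaries will present all subjects combined as a single treatment arm unless otherwise indicated".

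**The concern.** The protocol has a sentence written specifically for HADS that names the two epilepsy subpopulations. Following the SAP as written would produce no HADS table for either of them.

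HADS is the only dedicated mood scale with planned summaries. The C-SSRS (SAP 11.4.7) and psychiatric and mental status findings (SAP 11.4.5) are listed only. PGS subjects come from one of the four feeder studies and are described as a minority (Protocol 6.5; SAP 2.3). A pooled mean will therefore be driven by POS subjects, and a different course of anxiety or depression in PGS subjects would hardly show.

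**Working it through.** The plan states no figure to reproduce, so the check is mainly a comparison of texts.

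**Step 1. Does any other part of the SAP supply the split?**

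| Place | What it provides for HADS |
|---|---|
| SAP 3.1 and 3.6 | All subjects combined, unless stated otherwise |
| SAP 4.8 | Seizure type is a subgroup, but only where a later section calls for it |
| SAP 11.4.6 | Does not call for it |
| SAP 3.2.8 | Study visit cohorts depend on visit attendance, not on epilepsy type |
| SAP 3.5.2 | Assigns QOLIE-31-P and EQ-5D to the POS and PGS efficacy sets; HADS is not named |
| SAP 11 | Safety summaries use the Safety Analysis Set |

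None of these supplies it.

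**Step 2. Is the omission explained?** The SAP gives reasons when it drops other outputs: pharmacoeconomic variables (2.2.3), compliance (7) and C-SSRS (11.4.7). It gives none here, and the amendment section (14) does not mention HADS. The SAP does split by seizure type for disposition (5.1), demographics (6.1), exposure (11.1), the overall adverse event summary and common TEAEs (11.2.2), QOLIE-31-P (8.2.3) and EQ-5D (8.2.4).

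**Step 3. Is the protocol consistent with itself?** Not fully. Section 13.1.2 lists HADS among the other safety variables. In the same section, the variables to be assessed separately by epilepsy type include QOLIE-31-P and EQ-5D but not HADS. Section 13.1.3 bases the HADS analysis on the Efficacy Population, yet sends safety summaries to the Safety Population. It then adds the HADS-specific sentence on POS and PGS.

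**Step 4. How far would pooling dilute a PGS change?** Let *p* be the PGS share of subjects with a HADS change score:

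pooled mean change = *p* × (PGS change) + (1 − *p*) × (POS change)

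The documents give neither *p* nor any expected change, so every input here is an assumption. POS change is set to 0.

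- *p* = 0.05, PGS change 4 points: 0.05 × 4 = 0.2 points.
- *p* = 0.10, PGS change 4 points: 0.10 × 4 = 0.4 points.
- *p* = 0.02, PGS change 3 points: 0.02 × 3 = 0.06 points.
- *p* = 0.10, PGS change 3 points: 0.10 × 3 = 0.30 points.

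For scale, 2% and 10% of the 668 enrolled (SAP 2.4) are 668 × 0.02 ≈ 13 and 668 × 0.10 ≈ 67 subjects. The share among subjects with HADS data will differ from the enrolled share. N01193 subjects, all POS, do not complete HADS, which raises it. Mentally impaired subjects do not complete it either, and the effect of that is unknown.

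**The case against.** The best defence is that the SAP followed one of two protocol treatments. The protocol classes HADS as a safety variable and leaves it out of the list assessed separately by epilepsy type; the SAP pools HADS and splits QOLIE-31-P and EQ-5D, which matches those lists. The HADS sentence in 13.1.3 also lacks the word separately, which the protocol uses elsewhere when it means it, and POS and PGS together cover all the feeder studies. The SAP heading "Exploratory objectives for subjects with POS/PGS" is weak support for a split, since it says who is covered and not how results are shown.

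This stands as a reason to call the point a reconciliation. It does not remove it. A sentence that names two mutually exclusive subpopulations is most naturally read as asking for results in each, and it sits within the safety text, so classing HADS as a safety variable does not displace it.

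A reader might infer that PGS anxiety and depression could not be recovered at all. The documents do not support that: SAP 3.1 provides subject listings with source data and key derived variables, so PGS scores could be derived by hand. EQ-5D, which has an anxiety/depression dimension (Protocol 11.1.22), and the emotional well-being subscale of QOLIE-31-P are also summarized for PGS. A reader might also infer that the SAP plans a single pooled HADS summary; section 11.4.6 plans several, none by seizure type.

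Finally, HADS is not a primary variable, the study has one arm, and every summary is descriptive. The practical consequence is small.

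**Conclusion.** The point holds as a minor, unexplained mismatch. Protocol 13.1.3 calls for HADS in POS and PGS, SAP 11.4.6 provides no such tables, and nothing else in the SAP supplies or explains the difference. It would be too strong to say that the SAP breached a clear and uniform commitment, because the protocol itself treats HADS in more than one way.

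What is lost is a planned PGS summary table, not the PGS data. That the pooled tables would mainly reflect POS rests on PGS being a minority, which the documents state without a count. The shift of 0.2 to 0.4 points rests on an assumed 5% to 10% share, an assumed 4-point PGS worsening and no POS change. It shows how dilution works and does not predict a result.

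**What to change.** In SAP 11.4.6 add: *All HADS summaries will be given overall and by seizure type (POS, PGS).* In the same place, state which analysis set applies, so that Protocol 13.1.3 (Efficacy Population) and SAP 3.5.1 and 11.4.6 (Safety Analysis Set) no longer differ. If a pooled presentation is intended, record the departure from Protocol 13.1.3 with its reason.

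The cost is two SAP sentences and repeat tables from data already collected. PGS cells will be small and imprecise, which the SAP already accepts for QOLIE-31-P and EQ-5D.
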